8.3 Multivariate interference

It will be necessary to do a multivariate analysis adjusting the covariates according to the independent variable with the dependent variables that can interfere in the results, to avoid possible confusion.

Poisson regression model will be used for the association between the intervention and the number of reintubations, which is a **discrete quantitative variable**.

Cox regression models will be used for the association of the intervention with the **time** of weaning, which is a **continuous quantitative variable**. It is calculated as a survival analysis.

9. ETHICAL AND LEGAL CONSIDERATIONS

Ethical principles

The study will be performed under the requirements established by the World Medical Association (WMA) in the **Declaration of Helsinki** of Ethical Principles for Medical Research Involving Human Subjects (last revision in the 64th General Assembly, Fortaleza, Brazil, in October 2013) (65). This experimental study obeys the **Principles of Biomedical Ethics from Beauchamp and Childress** from 1970, reviewed in 2009, more commonly known as the four fundamental ethical principles:

- **Beneficence and non-maleficence:** Ensuring individuals are treated ethically, their decisions are respected, and they are protected from harm is the basis of beneficence. It is an obligation to ensure their well-being. In this study, all participants will receive invasive mechanical ventilation because they need it, and both weaning protocols used in this clinical trial are approved and used in clinical practice.
- **Justice:** To ensure that all individuals benefit from the research, we have established very inclusive and exclusive criteria and carefully selected a sample that we believe will benefit most from this intervention. Following the sampling phase, we have randomly assigned the protocol to ensure equal chances for all participants to receive a specific intervention.
- **Autonomy:** The recognition that people are autonomous and entitled to their own opinions and decisions. In this study, as the participants are neonates, the parents or legal guardians will be informed in detail about the study procedures, how data will be handled, and their right to be informed or to withdraw at any moment will be respected.

An **informative document** about the study protocol (see Annex 4) will be given to the parents or legal guardians of the patient in a language they can understand, in order to provide them with the necessary knowledge and understanding.

As this project involves neonates, parents or legally authorized representatives will be required to sign two reports: the first, giving the authorization to perform any intervention on the infant admitted to the NICU (see Annex 3); and the second, allowing the participation in our study, after providing comprehensive information. To express their agreement to participate in the study, they will sign the **informed consent form** (see Annex 5).

The autonomy of the participants is regulated by Spanish legislation: “**Law 41/2002, November 14th, regulating patient autonomy and right and obligations of information and clinical documentation**”. (66)

Privacy and confidentiality

All personal data collected from each patient during the study will be confidential, only for purpose of research and education; moreover, all data will be analysed anonymously, in accordance with the current legislation:

- Spanish data protection legislation: “**Organic Law 3/2018, of 5 December, on Data Protection and Guarantee of Digital Rights and the royal decree 1720/2007**”. (67)
- ***Regulation (EU) 2016/679 of the European Parliament and of the Council of 27 April 2016 on the protection of natural persons regarding the processing of personal data and on the free movement of such data.*** (68)

All newborns personal and clinical data collected in this study will be anonymous and confidential, as they will be identified by a **randomised code** generated by an electronic randomisation statistical software.

In addition, all data collected will **be available only to the research team** and will be used strictly for research purposes.

Comité d'Ètica i d'Investigació Clínica (CEIC)

The present project will be submitted to the CEIC of the *Hospital Universitari [name] (HUJT)*, whose suggestions given will be considered and whose approval will be mandatory before the start of the study. The system of controls to be carried out during the research will be in accordance with **Ley 14/2007, de 3 de julio, de Investigación biomédica**. (69)

Transparency

All investigators of this study will be required to declare no conflicts of interest. They will also have to agree to publish all data and results obtained with total transparency, including unfavourable data or events.

10. WORK PLAN AND CHRONOGRAM

10.1 Participating centres

The 5 centres proposed to carry out the study are the five with the highest incidence of extremely and very preterm newborns in Catalonia, according to the last study carried out.(64) Each hospital was assigned a number from 1 to 5.

10.2 Research team members

The personal required at the different stages of the clinical trial include:

- **Main investigator (MI) and director of research:** As director of research, he or she will direct the execution of the project, ensure the correct application of the protocol and the correct storage of the data. He or she will also participate in the discussion of the results, prepare the final report of the conclusions and their subsequent dissemination through the publication of the results.
- **Study Coordinator (SC):** As coordinator, he will be responsible for supervising the proper functioning of the other participating centres.
- **Hospital Coordinators (HC) – Head of co-investigators:** Each hospital will have a coordinator who will collect the data and ensure that the protocol is carried out correctly in his/her centre. They will facilitate coordination with the main investigator.
- **Co-investigators (CI):** These include expert intensivist; paediatricians; and **neonatologist experts**. The hospital coordinator and the neonatal expert can be the same professional. There will be co-investigators in each hospital.
- **Health Care Professionals (HCP):** Include all personnel needed to carry out this clinical trial, such as nurses or anaesthesiologists.
- **Data manager (DM):** She/he will manage the data collection during the study. He/she will be responsible for data processing, quality control and report writing for interim and final data analysis.

- **Statistical Specialist (SS):** The professional who will carry out the statistical analysis.
- **Other staff:** computer scientist, cleaning staff and other personal working in the hospital or involved in the process.

10.3 Study stages

The whole study will have an estimated duration of 44 months, which is equivalent to **3 years and 8 months**. The steps in this clinical trial will be performed in the following order, grouped into 6 stages, each consisting of different activities:

STAGE 0: Elaboration of the protocol and study design (4 months: September – December 2023)

1. **First session** (September 2023, completed): To discuss the project and to identify the gaps in information in this field of study.
2. **Bibliographical research and protocol elaboration** (September – November 2023): Includes the literature review and all practical considerations to elaborate the protocol. This phase will be carried out by the research members.
3. **Contact with the participating hospitals** (December 2023): the MI and SC will propose to the selected hospitals if they want to participate in the study. The protocol will be evaluated by the neonatologists, who will decide if they want to participate.

STAGE 1: Ethical approval (3 months: December 2023 – February 2024)

4. **Ethical evaluation and approval:** Presentation of the protocol to the research ethics committee (CEIC) of HUJT.

Any suggestions will be considered and modifications on the protocol will be made if necessary.

The length of this stage will depend on how long it takes for the CEIC to approve the study, an approximation of 3 months has been made.

STAGE 2: Coordination and health professionals training (2 months: March – April 2024)

- 5. First meeting with the research team** (March 2024): During this month, a date will be set for the first face-to-face meeting between the main investigator and the hospital coordinators of each centre. At this meeting, the different phases of the study, the timetable, the inclusion and exclusion criteria for patients, and the role of each investigator will be reviewed. An e-mail and/or telephone number will also be provided for better coordination. After this meeting, each hospital coordinator will be asked to hold a second meeting with all the co-investigators at his or her centre to provide them with the same information.
- 6. Formation sessions** (April 2024): An online meeting will be held with the whole team to provide theoretical training on neonatal resuscitation and neonatal mechanical ventilation. Particular emphasis will be placed on invasive mechanical ventilation and weaning. During this meeting, a consensual and detailed document will be sent to the hospital coordinators of each centre with the values of each parameter of the ventilator necessary for both the initiation of weaning and extubation. It will also include the clinical and gasometrical criteria for weaning, extubation and reintubation.

The aim of this training is to homogenise the process and reduce differences in the results between centres.

- 7. Creation of a database** (April 2024): A computer scientist will be hired to create a database, so that the data collected before, during and after the intervention can be correctly recorded.

STAGE 3: Sample recruitment, intervention, and data collection (27 months: May 2024 – July 2026)

8. Sample recruitment: As mentioned above, a consecutive stratified sampling method of extremely and very preterm newborns with NRDS that are on invasive mechanical ventilation, admitted to the NCIU of the participating hospitals will be carried out. Each co-investigator at each centre will be responsible for enrolling patients who meet all the inclusion criteria and any of the exclusion criteria, after the parents or legal guardians have signed the informed consent form (see Annex 5). Each participant will be randomised to one of the intervention groups of the clinical trial. The hospital coordinators of each centre will supervise this process.

Recruitment will continue until each centre has recruited the number of participants assigned by the stratification, with a 1:1 ratio. This is expected to take approximately 26 months (2 years and 2 months).

9. Intervention: During this period, patients will be assigned to one of the protocols for weaning, PSV in one arm of the study and ACVGV in the other.

This process can take a few days or even a few weeks, so an extra month has been added to the projected 26 months for this stage.

10. Follow up: After the intervention, all patients enrolled in the study will be followed for the first 72 hours after extubation, as all clinical data will be recorded in the baby's medical record.

11. Data registry: As the patients are enrolled and followed up, the researchers will record the data of each variable to be studied in the data form to be later entered into a database shared by the 5 hospitals.

This will be done by the HC or the neonatologist expert of each hospital.

Sample recruitment will take place in parallel with the intervention and follow up, as some patients will be undergoing the intervention while others are being recruited or followed up.

The newborns will be enrolled in the study while they are on invasive mechanical ventilation. Once they meet the criteria to start weaning, the intervention will start, and patients will be randomised to one of the two protocols: PSV or ACVGV. When the patient meets the criteria for extubation, the intervention is concluded, and a 72-hour follow up will begin.

While the data is registered, the data manager will be responsible for data processing, quality control and report writing for interim and final data analysis.

During this stage, three-monthly online meetings led by the principal investigator and the data manager will be held with the hospital coordinators of each participating hospital, with the aim of facilitating communication between centres, assessing compliance with deadlines, notifying problems that have occurred during this time and being able to solve them as quickly as possible.

STAGE 4: Statistical analysis and data interpretation (4 months: August – November 2026)

12. Statistical analysis (August – October 2026): During this period, statistical analysis of the data will be performed by a subcontracted statistician, who will analyse all the data collected by descriptive, bivariate, and multivariate analysis. He or she will be blinded to the study groups.

13. Results and conclusions (November 2026): The statistician will present the results to the whole research team, who will discuss the outcomes and draw conclusions.

STAGE 5: Results publication and dissemination (5 months: December 2026 – April 2027)

14. Article writing, revision, and publication (December – February 2027): The MI will write the final article with the results and conclusions. It will be edited and supervised by English correctors and published afterwards.

15. Dissemination (March – April 2027): The written study will be published as a journal article. National and international congresses will be attended to present the results.

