7.2 Study population

Inclusion criteria

- Preterm neonate, born at less than 32 weeks of gestation.
- Must be on invasive mechanical ventilation due to neonatal respiratory distress syndrome.
- Informed consent signed by parent or legal guardian.

Exclusion criteria

- Any congenital malformations
- Any chromosomopathies
- Any cardiopathies
- Any neurological malformations

These criteria have been selected because all of these pathologies can affect the patient's respiratory pattern, so it is possible that newborns with these criteria may have different management necessities, more time on mechanical ventilation, or more complications related to their underlying pathology.

Withdrawal criteria

- **Request to revoke consent for the study:** the parents or legal guardians of the neonate can express voluntary decision to be excluded from the study at any point. (see Annex 6)
- **Neonates' death:** from enrolment until the end of the follow-up period.

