7.5 Study intervention

In this study there will be two different protocols applied for weaning of invasive mechanical ventilation in extremely and very preterm newborns with NRDS: PSV and ACVGV. These protocols will be applied by professional neonatologists.

When an extremely or very preterm newborn is in invasive mechanical ventilation due to NRDS and meets all inclusion criteria and any exclusion criteria, an informative document (see Annex 4) and an informed consent (see Annex 5) will be given to the parents or legal guardians to sign.

Once the newborn enters the study, the neonatologists will wait until this patient meets the **criteria to start the weaning**. These criteria will be **precisely explained** in the document given to all hospital coordinators during the formation sessions. The weaning criteria are the following:

- Clinical criteria:
 - o Stable patient
 - o No intercurrent process that may hinder weaning

- Respirator parameters
 - o $FiO_2 < 40$ mmHg
 - o $PEEP < 7$ cmH₂O
 - o $RR < 50$ rpm
 - o $PIP < 20$ cmH₂O

When the patient meets the weaning criteria, the intervention will start. The intervention will be carried out by a neonatology expert. The patient will be randomly assigned in one of the two groups:

- o Group 1: The protocol used for the weaning will be **pressure support ventilation (PSV)**

- o Group 2: The protocol used for the weaning will be **assist control volume guarantee ventilation (ACVGV)**

Both protocols of weaning have been properly explained in section 3.3.3 *Invasive mechanical ventilation*.

The patient will remain in weaning until he or she meets the **criteria for extubation**. These criteria will be **precisely explained** in the document given to all hospital coordinators during the formation sessions. The patient will be extubated to a CPAP with a nasal PEEP of 6 mmHg. The extubation criteria are the following:

- Gasometrical criteria:
 - o pH > 7,3
 - o pCO₂ < 50 mmHg
 - o pO₂ > 70 mmHg
 - o Sat Hb 90-95% (haemoglobin saturation)

- Clinical criteria:
 - o Stable patient
 - o Without active infectious process
 - o Without hemodynamically significant ductus
 - o Neurologically capable of maintaining a patent airway

- Respirator parameters:
 - o PEEP < 6 mmHg
 - o FiO₂ < 30 cmH₂O
 - o RR < 20 rpm
 - o PIP < 20 cmH₂O
 - o Tidal volume 5 ml/kg

[figure not shown]

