7.6 Flow chart

7.7 Data collection

All baseline and outcome data will be collected prospectively using a data collection form. This data form has been designed to collect all clinical and procedural information (see Annex 7) from the different NICUs participating in this project.

Each patient will be identified with a special ID to maintain anonymity, the patient's name cannot appear. Once a week, the neonatologist expert or hospital coordinator of each hospital must collect all the files gathered by the neonatologists of his/her hospital and add them to an online database. When the statistical specialist analyses the database, he/she will not know the name of the baby, or the technique used.

A data quality control service will be contracted to supervise the process and ensure correct data collection.

Period 1: Inclusion and baseline data

The main investigator will contact potential participants to evaluate if they meet all the inclusion criteria and any exclusion criteria. This will take place in the NICU, when there is a preterm infant with NRDS on invasive mechanical ventilation.

If the patient meets all the study criteria, an information form (see Annex 4) and an informed consent (see Annex 5) will be given to the parents after proper explanation.

When the patient is already part of the study, the researcher will proceed with the collection of baseline data, corresponding to the covariates.

Period 2: Intervention period

A baseline researcher, not involved in the outcome assessment, will be responsible for assigning the ID code to each participant. In addition, this

researcher will distribute to the neonatologist the randomised allocation prepared by the biostatistician, indicating the protocol he/she will use.

During the intervention, the baseline researcher must ensure that all dependent variables related to the intervention are collected.

Period 3: Follow up

After 72 hours of the intervention, the baseline researcher not involved in the outcome assessment will evaluate the dependent variable (reintubation).

Once completed, the data form must be sent to the hospital coordinator or neonatologist expert who will add the data to the general online database.

Later, when all the data from all the participants is completed, it will be sent to the statistician expert for analysis.

Figure 18 - Summary of the data collection process

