12. LIMITATIONS AND STRENGTHS

12.1 Limitations

There are some limitations in the protocol that need to be considered for future analysis and extrapolation of results.

Selection bias

The first potential source of bias relates to the **recruitment of the sample**. Consecutive sampling will be used, which is a non-probabilistic method. Therefore, there is a possibility of not obtaining the most representative population. In order to mitigate this selection bias and to ensure strong external validity, extensive inclusion criteria have been formulated, while exclusion criteria have been designed to reduce any confounding factors. We are aware that the sampled population may not mirror the general population. However, we consider that it is closer to the real target population that may benefit from the final results.

The second bias in the selection phase is the **participation rate**, as we assume that two years and two months of recruitment will be enough to achieve an ideal number of people to do the intervention. If this is not the case, we could extend the selection period. Another approach is to add another study centre, an option that does not pose any major challenges as the study is multicentred.

Methodological bias

The study can be an important step to prioritize one weaning protocol over the other. Although the inclusion criteria prevent the generalization of the results to all neonates, it is expected that if the results are satisfactory, a new study could be designed including neonates > 32 weeks of gestation.

It is a clinical trial that studies two different weaning protocols in preterm infants, so it is impossible to be a double-blinded design. To reduce the **detection bias**, the statistical specialist will be blinded to the participants' intervention.

Personal bias

As this is a multicentre trial, there is a potential for **performance bias**. After the child is born, a different neonatologist will attend the newborn, depending on the hospital, the day, and time of birth. This can lead these preterm newborns being treated differently regarding first minute's reanimation, a very important moment for the future outcome. To reduce this performance bias, all professionals participating in the study will receive theoretical training in which they will all be given the same indications.

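### Sections 7.5 and 10.3 state the exclusion rule the wrong way round (all inclusion and *any* exclusion criteria); section 7.7 is ambiguous, and the text nowhere says *none*

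*Combined protocol and SAP*

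**What the plan says.** Section 7.2 gives three inclusion criteria and four exclusion criteria: congenital malformations, chromosomopathies, cardiopathies and neurological malformations. It says the exclusions were chosen "because all of these pathologies can affect the" infant's breathing pattern, and that "newborns with these criteria may have different management necessities, more time on mechanical ventilation, or more complications related to their underlying pathology". Section 12.1 repeats the purpose under selection bias: the "exclusion criteria have been designed to reduce any confounding factors". Under confounding bias it again counts the exclusions among the preventive measures.

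Three later places apply the criteria:

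- Section 7.5 (Study intervention): the information sheet and consent form go to the parents when the infant "meets all inclusion criteria and any exclusion criteria".
- Section 7.7 (Data collection, Period 1): the main investigator approaches potential participants to "evaluate if they meet all the inclusion criteria and any exclusion criteria". Consent follows if the study criteria are met.
- Section 10.3 (Stage 3, item 8): each co-investigator is responsible for enrolling infants who "meet all the inclusion criteria and any of the exclusion criteria", once consent is signed.

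Section 7.1 mentions only the inclusion criteria when it describes selection.

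**The concern.** Sections 7.5 and 10.3 are working steps: one triggers the offer of consent and the other assigns the enrolment task. Taken at their word, both require at least one exclusion condition to be present. That is the reverse of section 7.2 and would select the infants whom the plan wants to keep out because their course on ventilation may differ.

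What is at stake is mainly the integrity of the eligibility rule as a standard. Monitors and the ethics committee judge enrolment against the protocol. If two of its sections contradict a third, the same infant can be both eligible and a protocol deviation, depending on which section is cited.

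**Working it through.** No arithmetic bears on the point itself, so the check is a comparison of the text.

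**Step 1: put each statement in logical form.** Let *I* mean that all three inclusion criteria are met, and *E* that at least one of the four exclusion criteria is met.

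| Place | Function | Literal rule |
|---|---|---|
| 7.2 | Defines the population | *I* and not *E* |
| 7.5 | Offer of consent | *I* and *E* |
| 7.7, Period 1 | Screening | *I* and *E*, or a check of *I* and of *E* |
| 10.3, item 8 | Enrolment | *I* and *E* |

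**Step 2: compare.** The sets (*I* and not *E*) and (*I* and *E*) do not overlap. An infant correctly enrolled under 7.2 fails the literal wording of 7.5 and 10.3, and an infant who satisfies that wording violates 7.2.

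**Step 3: test each passage for a harmless reading.** In 7.7 the verb is to evaluate, so the sentence can mean looking at the inclusion list and at whether any exclusion applies. In 7.5 and 10.3 the phrase describes the infant who is offered consent or enrolled, and the screening reading does not fit. Two passages are therefore wrong and one is ambiguous.

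**Step 4: look for a correct statement elsewhere.** The text contains no sentence saying that an infant must meet none of the exclusion criteria. The flow chart in section 7.6 is not shown in the copy reviewed, so this covers the text only.

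**Step 5: look for a check in the data.** The Annex 7 form has fields for the infant, the mother, the pregnancy and the intervention. None records the four exclusion conditions; the one congenital item concerns the mother's uterus. The four conditions are not among the covariates in section 7.4 either. The trial data set would not show whether an enrolled infant had an exclusion condition.

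**Step 6: check the sample size.** Section 7.3.1 uses a 16% reintubation proportion, a difference of 0.1 (read here as 10 percentage points, 16% against 26%), two-sided alpha 0.05, beta 0.2 and 5% drop-out. With the arcsine formula, n = 2 × [(1.960 + 0.842) / h]², where h = 2·asin(√0.26) − 2·asin(√0.16) = 0.247. This gives n = 257.1, and 257.1 / 0.95 = 270.6, which rounds up to the stated 271 per group. No input depends on the exclusion wording.

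**The case against.** The strongest reply is that this is a copy-editing matter. The intent is not in real doubt: the list stands under an exclusion heading, section 7.2 gives the reason for it, and section 12.1 repeats the purpose twice. A condition that must be present for entry is not an exclusion criterion, so the literal reading defeats itself. The recruitment estimate in section 7.3.3 starts from all infants with the syndrome who need invasive ventilation, about 257 per year, and not from a subgroup with malformations. One slip repeated in three places is more plausible than three deliberate rules.

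The protocol also has safeguards. In section 10.3, hospital neonatologists evaluate the protocol before joining, the ethics committee may ask for changes, the first team meeting reviews the inclusion and exclusion criteria with every hospital coordinator, and the coordinators pass this on to their co-investigators and supervise recruitment.

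Most of this stands, and it limits the weight of the point. It does not remove it. The meeting can explain the rule but does not amend the text against which enrolment is audited. The detailed document for coordinators is described as covering weaning, extubation and reintubation; eligibility is not among its listed contents.

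A reader might go further and infer that the five hospitals are left to guess which section governs, that the whole sample would be ineligible, or that occasional wrong enrolments should be expected. The documents support none of these. Section 7.2 points to the right reading, a review of the criteria with all centres is scheduled, and nothing in the text gives a basis for a rate of wrong enrolment.

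**Conclusion.** The point holds as an error in operative wording. Sections 7.5 and 10.3 state the eligibility rule in reverse, section 7.7 is ambiguous, and all three need to agree with section 7.2. The most likely explanation is a language slip for *none of the*; the passages are not evidence that a different population is intended.

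The practical risk is low, and no effect on bias, power or the estimate can be shown from the documents. The sample size is unaffected. What remains is that the rule assigned to those who enrol is wrong as written and cannot be audited consistently against section 7.2. The conclusion assumes that section 7.2 expresses the intended population, as its rationale and section 12.1 indicate, and that the flow chart in section 7.6 does not carry a correct statement that would override the text.

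**What to change.** In sections 7.5, 7.7 (Period 1) and 10.3 (Stage 3, item 8), replace *any* or *any of the* before *exclusion criteria* with *none of the*, and refer to the list in section 7.2: congenital malformations, chromosomopathies, cardiopathies and neurological malformations. In section 7.7 this also removes the ambiguity. Check that the flow chart in section 7.6 says the same.

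The cost is a few words in three places, with no effect on population, design, analysis or budget. As an optional addition, one line on the Annex 7 form confirming that no exclusion criterion is met would let the corrected rule be verified from the trial data.
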